### 3.4. Statistical framework

For each trial, we propose two primary analyses:

- Comparison of oral valganciclovir and placebo arms (superiority comparison)
- Comparison of oral valganciclovir and topical ganciclovir 2% arms (superiority comparison)

Analyses of the trials will be intention to treat, with participants analyzed as they are randomized. We plan to use a frequentist approach to the analysis, with appropriate control for multiple testing and any interim analyses (details below).

### 3.5. Statistical interim analyses and stopping guidance

The interim analysis for both efficacy and futility will be conducted after one-third (1/3) and before one-half (1/2) of the patients have reached their primary endpoint; ideally when there are 15 patients per arm. With three arms and two primary comparisons of interest there are several scenarios for each interim analysis (Tables 2 and 3). The pre-specified action taken under each scenario will be agreed upon at the trial's first DSMC meeting. Separate interim analyses will be conducted for Trial I and Trial II, but will proceed similarly.

The DSMC will make one of the following recommendations:

- Continue the study without modifications
- Continue the study with modifications
- Terminate enrollment or treatment in the study because of safety concerns
- Terminate enrollment or treatment in the trial because of futility

The DSMC will determine the database closure dates for each report in advance; archival copies of the (a) main database, and (b) study analysis file as they exist at the time of each report will be maintained. All reports will be sent using secure email to the members of the DSMC two weeks prior to each meeting.

Table 2. Treatment Arms

Arm 1: Oral valganciclovir	Arm 2: Ganciclovir 2% eyedrop	Arm 3: Placebo
A	B	C

Table 3. Possible Scenarios in Interim Analysis for Efficacy

Scenario	Trial I/II interim result	Trial I/II interim result	Action for Trial I	Action for Trial II
	A vs B	A vs C		
1	A ~ B	A ~ C	Continue all arms	Continue all arms
2	A ~ B	A < C	DSMC discussion 	DSMC discussion 
3	A ~ B	A > C	DSMC discussion 	DSMC discussion 
4	A < B	A ~ C	DSMC discussion 	DSMC discussion 
5	A < B	A < C	DSMC discussion 	DSMC discussion 
6	A < B	A > C	DSMC discussion 	DSMC discussion 
7	A > B	A ~ C	DSMC discussion 	DSMC discussion 

DSMC discussion will be triggered in such a scenario to discuss the continuation or cessation of arm(s). Pre-specified actions for each scenario will be agreed upon between the investigators and the members of the DSMC at the trial's first DSMC meeting.

The DSMC will make decisions with the benefit of pre-specified decision guidelines. These guidelines will be agreed upon at the initial meeting, and are expected to include (a) safety, (b) efficacy, and (c) futility.

Safety. Stopping for harm will be done at the judgment of the DSMC. Several endpoints will be examined, including adverse events, and especially abnormal lab results meeting the designated threshold of a serious adverse event.

All subjects who provide informed consent will be accounted for in this study. We will present the number lost to follow-up and the number of protocol deviations by arm. The proportion of subjects reporting adverse events and serious adverse events will be reported by arm to the DSMC and will be compared using a Fisher's Exact Test.

Efficacy. Unmasked interim analyses will be conducted to determine whether or not sufficient evidence has accumulated to justify stopping the trial because one treatment is clearly superior

(and therefore should be extended to all future cases). The guidelines for efficacy will use group sequential boundaries for judging the statistical significance of the primary outcome measure. The Lan and DeMets flexible alpha spending approach with a power function is suggested, with  $a^*(t^*) = a(t^*)\Theta$ , where  $q=3.561$  chosen so that the two-sided P-value to stop the trial for efficacy is 0.0005 for each comparison.

Futility. Early discontinuation due to the unlikeliness of significant findings conditional on interim results may be considered, based on the original sample size considerations. For evaluating futility in each trial, we propose to use a simulation-based approach that estimates conditional power under the assumed design effect for the remainder of participants and under the current trend observed at the interim analysis. We propose that the DSMC consider discontinuation for futility if the conditional power to detect a difference in viral load in Trial I and recurrence in trial II drops below 20% at the interim analysis under the assumed design effect for the remainder of participants yet to be enrolled. As for the efficacy analysis, the futility analysis will be conducted separately for each Aim/hypothesis. Our proposed futility guidance is one-sided, and is subordinate to efficacy analyses. We will not propose to discontinue an arm for futility at the interim analysis if that arm may still participate in an efficacy comparison.

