- Laboratory screening orders (CBC, chemistry panel, pregnancy test, HIV status)
- Patients will be prescribed topical corticosteroid (prednisolone acetate 1%) to be used one drop in affected eye four times per day (this is typical standard of care)
- Patients requiring management of elevated IOP will be prescribed IOP-lowering medication according to treating ophthalmologist's discretion and best medical judgment

Exam 1 Randomization and Procedures

[figure not shown]
- Review of results of in- house CMV PCR and laboratory results
- Consent, enrollment, randomization to treatment arm if participants meet eligibility criteria
- Clinical eye examination (in the following order: visual acuity, slit lamp examination of anterior segment, intraocular pressure assessment, confocal microscopy)

Randomization to 1 of 3 arms

Exam 2 (Day 7) Follow-up

- Clinical eye examination (in the following order: visual acuity, slit lamp examination of anterior segment, intraocular pressure assessment)
- **Anterior chamber paracentesis #2**
- **Assessment of clinical quiescence (grading anterior chamber cell)**
- Laboratory monitoring orders (complete blood count, complete metabolic panel)

Exam 3 (Day 21) Final visit for trial I

Trial II

**Exam 1
(Re-randomization)**

Clinically inactive (< 1+ anterior chamber cell)
for at least 2 weeks with at least 2 weeks
wash-out period (no antivirals)

- Clinical eye examination (in the following order, VA, slit lamp examination of anterior segment, IOP)
- **Suppressive treatment initiation (randomized to 1 of 3 arms)**

Group 1: Oral
valganciclovir N=35

Group 2: Topical
ganciclovir 2% N=35

Group 3: Placebo
N=35

**Exam 2
(1 month after
randomization)**

- Clinical eye examination (in following order, VA, slit lamp examination of anterior segment, IOP)
- **Assessment for recurrence of inflammation**
- **Anterior chamber paracentesis #3 if recurrent inflammation (participant exits study if recurrent inflammation)**

**Exam 3
(3 months after
randomization)**

- Clinical eye examination (in following order, VA, slit lamp examination of anterior segment, IOP)
- **Assessment for recurrence of inflammation**
- Confocal or specular microscopy if recurrent
- **Anterior chamber paracentesis #3 if recurrent inflammation (participant exits study if recurrent inflammation)**

**Exam 4
(5 months after
randomization)**

- Clinical eye examination (in following order, VA, slit lamp examination of anterior segment, IOP)

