- **Assessment for recurrence of inflammation**
- Confocal or specular microscopy if recurrent
- **Anterior chamber paracentesis #3 if recurrent inflammation (participant exits study if recurrent inflammation)**

**Exam 5
(7 months after
randomization)**

- Clinical eye examination (in following order, VA, slit lamp examination of anterior segment, IOP)
- **Assessment for recurrence of inflammation**
- Confocal or specular microscopy if recurrent
- **Anterior chamber paracentesis #3 if recurrent inflammation (participant exits study if recurrent inflammation)**

**Exam 6
(9 months after
randomization)**

- Clinical eye examination (in following order, VA, slit lamp examination of anterior segment, IOP)
- **Assessment for recurrence of inflammation**
- Confocal or specular microscopy if recurrent
- **Anterior chamber paracentesis #3 if recurrent inflammation (participant exits study if recurrent inflammation)**

**Exam 7
(11 months after
randomization)**

- Clinical eye examination (in following order, VA, slit lamp examination of anterior segment, IOP)
- **Assessment for recurrence of inflammation**
- **Anterior chamber paracentesis #3 if recurrent inflammation (participant exits study if recurrent inflammation)**

Exam 8
(12 months after
randomization,
Final Visit)

- Clinical eye examination (in the following order, VA, slit lamp examination of anterior segment, IOP)
- **Assessment for recurrence of inflammation**
- **Anterior chamber paracentesis #3 if recurrent inflammation (participant exits study if recurrent inflammation)**

Note that participants will be advised to contact their local site clinical coordinator or study ophthalmologist if they are having symptoms of recurrent inflammation. Recurrent inflammation is typically symptomatic (characterized by ocular redness, decreased vision, light sensitivity, and pain). Thus, participants will be evaluated for symptoms of recurrent inflammation, which may occur between study visits, during which they would have clinical eye examination, anterior chamber paracentesis #3 (if there is recurrent (active) inflammation).

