**Primary analysis for Trial II.** The primary outcome for Trial II is the proportion of participants experiencing CMV recurrence over 12 months. We acknowledge that hypothesizing fewer recurrences in the placebo group compared to the oral antiviral group is contradictory to what one might think would typically occur with exposure to antivirals. However, data from a previous observational study showed a one-year recurrence risk of 25.0% (3/12) among participants who did not receive antiviral treatment and 75.0% (9/12) in participants receiving systemic antiviral treatment (oral ganciclovir or valganciclovir), which is similar to the experience of other research. Additionally, it is well documented that long-term suppressive-level dosing of antiviral in an immunodeficient host or in an immunologically privileged organ (such as the eye) can create an environment permissive to the development of antiviral resistance. Given 28 participants per arm (105 total from Trial I with 20% loss to follow-up) and a recurrence risk of 25% in the placebo group, we can detect a difference of 40 percentage points between the oral valganciclovir and the placebo groups (from 25% to 65%), using a two-sample z-test for proportions with 80% power and a two-sided alpha of 0.05/2.

**For Specific Aim 3,** we estimated the minimum detectable effect for the difference in prevalence of infections that have antiviral resistance mutations among recurrent infections in Trial II among patients who receive long-term antiviral prophylaxis compared with their infections at baseline. Aim 3 will focus on patients in the two active treatment arms in Trial II, because we would expect long-term use of topical and oral antivirals to lead to similar selection for antiviral resistance. From 117 patients enrolled, we conservatively assumed that 72% of patients would complete both Trial I and Trial II (n=84). We further assumed that 60% of patients will develop a recurrent infection over the monitoring period during the trials (Table 1). Participants who receive active treatment in Trial II (treatment regimens C+D) will contribute to the Aim 3 analysis (n=34). The analysis will be a paired analysis, comparing the proportion of recurrent infections with antiviral resistance mutations with that same proportion at baseline.

Table 1. Anticipated participant enrollment, and follow-up by treatment patterns

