### Primary Analysis Trial II

**Aim 2a. Recurrence rate of anterior uveitis over 12 months:** The proposed analysis for sub-Aim 2a (Trial II), which is a clinical outcome, is a log-binomial regression model to compare cumulative inflammatory recurrence (based on anterior chamber cell  $\geq 1+$  cell) between treatment groups. We will censor participants at the first recurrence of anterior uveitis (based on anterior chamber cell  $\geq 1+$  cell) or 12 months. The model includes indicators for the treatment arm and indicators for each site used to stratify the randomization. We will estimate the risk ratios from the model for the two primary comparisons, *oral valganciclovir* vs. *topical ganciclovir 2%*, and *oral valganciclovir* vs. *placebo*. We will use a simulation-based permutation test to estimate p-values, and will report max-T simultaneous confidence intervals and p-values adjusted for the two pair-wise comparisons (*oral valganciclovir* vs. *topical ganciclovir 2%*, *oral valganciclovir* vs. *placebo*). Pre-specified sub-group analyses by sex will be performed.

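### Trial II compares adverse events as crude proportions although participants leave at first recurrence, so any difference in recurrence between arms distorts the safety comparison

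*SAP*

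**What the plan says.** The Safety paragraph of SAP 3.5 has the proportions of subjects with AEs and with SAEs "reported by arm to the DSMC and will be compared using a Fisher's Exact Test". Protocol 8.3.1 says the same. No other comparative safety method appears in either document. SAP 6.5 only tabulates AEs, and SAP 4.2 puts anyone with at least one dose in the safety population, however long they were observed.

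The Trial II schema in the Protocol synopsis repeats at each follow-up exam that the "participant exits study if recurrent inflammation". No AE follow-up after that exit is described. The instruction in Protocol 7.2.4 to continue visits applies after an SAE, not after a recurrence.

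The plan does recognise unequal follow-up for efficacy. SAP 6.2 states "We will censor participants at the first recurrence of anterior uveitis" (or at 12 months) and adds an exploratory Cox model for time to recurrence.

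SAP 3.3 sizes Trial II with 28 per arm, which allows for 20% loss from 35. Its detectable alternative is worded as "a recurrence risk of 25% in the placebo group, we can detect a difference of 40 percentage points". The oral valganciclovir risk at that alternative is therefore 65%.

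**The concern.** Comparing the proportion with at least one event is fair only if the arms are watched for similar lengths of time. In Trial II the length of observation is set by the primary outcome. Under the plan's hypothesis, recurrences are more frequent on oral valganciclovir, the arm for which Protocol 2.3.1 lists systemic toxicity. That arm would be observed for less time and would look safer than it is. If prophylaxis prevents recurrences, the oral arm would be observed for longer and would look more harmful than it is. Either way, the AE proportions given to the DSMC mix toxicity with efficacy, and nothing in the plan separates the two.

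**Working it through.** **Inputs.** Recurrence over 12 months of 25% (placebo) and 65% (oral), with 28 per arm after 20% loss from 35 (SAP 3.3). Range for the oral arm: 61% (Protocol 8.2, 25% plus 36 points) and 75% (the observational figure in SAP 3.3). The documents give no AE rate, so AE risks below are assumptions shown over a range.

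**The plan's own figure.** A two-sample z-test with 28 per arm, 25% against 65%, two-sided alpha 0.025, has 79.9% power, and the solved detectable difference is 40.0 points. The SAP's figure reproduces.

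**Observation time.** With a constant recurrence hazard m = −ln(1 − risk) per year, mean observation over 12 months is 12 × risk / m.
- Placebo: m = −ln(0.75) = 0.288; 12 × 0.25/0.288 = 10.4 months.
- Oral: m = −ln(0.35) = 1.050; 12 × 0.65/1.050 = 7.4 months.
- Ratio 1.40.

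**Observed AE proportion.** With constant AE rate a, independent of recurrence, P(AE seen) = a/(a + m) × (1 − exp(−(a + m))).
- Identical AE rates, 20% risk over a full 12 months (a = 0.223): 17.5% on placebo, 12.6% on oral.
- Oral-to-placebo rate ratio at which the two proportions are equal: 1.42, 1.44 and 1.49 for placebo 12-month AE risks of 10%, 20% and 40%.

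**Sensitivity of the 1.40 observation-time ratio.**

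| Assumption | Ratio |
|---|---|
| Oral recurrence 61% | 1.34 |
| Oral recurrence 75% | 1.61 |
| 65%, recurrences spread evenly over the year | 1.30 |
| 65%, recurrences found only at scheduled visits | 1.33 |
| 65%, 20% dropout added | 1.38 |
| 65%, front-loaded recurrence (Weibull shape 0.7; 10.2 vs 6.7 months) | 1.51 |
| 65%, AEs only in the first 3 months | 1.10 |
| 65%, AEs only in month 1 | 1.03 |

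**How candidate tests behave.** Simulation with 35 per arm, recurrence 25% against 65%, nominal two-sided 5%. The last row covers placebo AE risks of 20% and 40%; the others use 20%.

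| Scenario | Fisher | Exact person-time rate test | Log-rank, time to first AE |
|---|---|---|---|
| True threefold constant AE rate | 21% | 58% | 61% |
| Equal rates, constant hazard | below 5% | below 5% | near 5% |
| Equal hazards, AEs only in first 1 to 3 months | 2 to 4% | 8 to 18% | near 5% |

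Without exit at recurrence, Fisher's test would reject in about 65% of trials in the threefold case, so most of its loss comes from unequal exposure.

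**A remedy that does not work.** Cumulative incidence of AE with recurrence as a competing event estimates the probability of an AE before recurrence. Without other dropout, that is the formula for P(AE seen) above, and it returns the same 17.5% and 12.6%.

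**The case against.** Several counter-arguments have force.

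- **65% is a detectable alternative, not a forecast.** This stands. The distortion depends on a recurrence difference that the trial has yet to show, and with equal recurrence it vanishes.
- **The 1.4 needs a constant AE hazard.** This stands. The documents give no AE timing, and early clustering almost removes the effect. Blood tests are, however, scheduled at Trial II Exams 2 to 7 (months 1 to 11), so the plan looks for toxicity all year.
- **A person-time rate test has its own bias.** This stands. With early AEs and equal hazards it rejects too often, so it should not simply replace Fisher's test.
- **The direction is not certain.** Protocol 7.2.1 counts raised intraocular pressure and worsening of an existing condition as AEs. If flare findings are recorded as AEs, the arm with more recurrences looks worse, not safer.
- **A 1.4-fold rate would go undetected anyway.** With full follow-up, Fisher's test would detect it in about 6% of trials at 20% placebo risk. The harm is therefore a misleading comparison of proportions more than a missed significant result.

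A reader might also infer that the DSMC's harm decision rests on Fisher's test, or that the final safety conclusion must carry the same bias. The documents do not support either. SAP 3.5 leaves stopping for harm to the DSMC's judgment over several endpoints, Protocol 7.2.5 sends it SAEs by arm every month, and SAP 6.5 names no final comparative test. But the monthly SAE report is not said to include exposure, and judgment is better served by a comparison that does not move with the primary outcome.

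**Conclusion.** The point holds for Trial II only; Trial I has fixed visits to day 21 and no exit at recurrence. The sole comparative safety analysis ignores observation time in a trial where the primary outcome ends observation. At 25% against 65% recurrence, with constant hazards and AEs unrelated to flares, a true oral AE rate about 1.4 times placebo would show as equal proportions. The range is about 1.3 to 1.6 across the plan's other recurrence figures and hazard shapes, and 1.03 to 1.10 if AEs cluster in the first one to three months.

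The stronger reading, that the plan will hide a 1.4-fold excess on oral valganciclovir, is not supported: the size and even the sign depend on the recurrence result, on AE timing and on whether flares count as AEs. This is an inexpensive improvement to the safety analysis. It does not touch the primary efficacy test.

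**What to change.** In SAP 3.5 and Protocol 8.3.1, for Trial II only:

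1. Keep crude counts and proportions by arm as description.
2. Report treatment and observation time by arm. Events per person-month may be added as description.
3. Make the comparative analysis time to first AE and time to first SAE, by Kaplan-Meier with a log-rank test or a Cox hazard ratio with confidence interval, censored at study exit. The log-rank test needs no constant AE hazard. It does need exit to be unrelated to AE risk, hence item 4.
4. State whether recurrences and flare-related findings count as AEs, and analyse AEs with these excluded.
5. Do not use cumulative incidence with recurrence as a competing event as the remedy.

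SAP 6.5 should name the same method for the final report. Fisher's test can stay for Trial I.

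Cost: a wording change in both documents and slightly more analysis work, with no extra participants or visits. Protocol 7.2.5 specifies an onset date only for SAE reports, so if the AE log lacks one for non-serious AEs, that field must be added.

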8.3.1 SAFETY ANALYSES

Interim reports for the DSMC will be prepared by the central Proctor site.

The Data and Safety Monitoring Committee will meet to review the interim efficacy data when primary outcome data is available on one third of the study subjects. The DSMC will make one of the following recommendations:

- Continue the study without modifications
- Continue the study with modifications
- Terminate enrollment or treatment in the study because of safety concerns
- Terminate enrollment or treatment in the trial because of futility

The DSMC will determine the database closure dates for each report in advance; archival copies of the (a) main database, and (b) study analysis file as they exist at the time of each report will be maintained. All reports will be sent using secure email to the members of the DSMC two weeks prior to each meeting.

The DSMC will make decisions with the benefit of pre-specified decision guidelines. These guidelines will be agreed upon at the initial meeting, and are expected to include (a) safety, (b) efficacy, (c) futility, (d) clinical importance, or (e) validity.

Efficacy. Unmasked interim analyses will be conducted to determine whether or not sufficient evidence has accumulated to justify stopping the trial because one treatment is clearly superior (and therefore should be extended to all future cases). The guidelines for efficacy will use group sequential boundaries for judging the statistical significance of the primary outcome measure. The Lan and DeMets²³ flexible alpha spending approach with a power function is suggested, with $\alpha^*(t^*) = \alpha (t^*)^\theta$, where $\theta = 3.561$ chosen so that the two-sided *P*-value to stop the trial for efficacy is 0.001.

Harm. Stopping for harm will be done at the judgment of the DSMC. Several endpoints will be examined, including adverse events, and especially abnormal lab results meeting the designated threshold of a serious adverse event.

All subjects who provide informed consent will be accounted for in this study. We will present the number lost to follow-up and the number of protocol deviations by arm. The proportion of

subjects reporting adverse events and serious adverse events will be reported by arm to the DSMC and will be compared using a Fisher's Exact Test.

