## **4. Statistical Principles**

### **4.1. Confidence intervals and P-values**

The primary analysis for Trial I and Trial II will be conducted with a two-sided alpha of 0.05/2 = 0.025 to account for the two primary comparisons of interest (*oral valganciclovir* vs. *topical ganciclovir 2%*, *oral valganciclovir* vs. placebo). We will report 95% confidence intervals for the estimated differences between groups, on an absolute scale.

We will use a single-step, max-T approach to estimate p-values adjusted for multiple comparisons in each analysis. Alongside unadjusted p-values and 95% confidence intervals, we will present max-T adjusted p-values and simultaneous 95% confidence intervals for differences that account for multiple comparisons.

We will employ a multiple testing hierarchical approach in the following manner:

1. Primary endpointss (alpha = 0.025 each trial)
  - a. Trial I: viral load comparison
  - b. Trial II: Number of recurrences comparison
2. Key secondary endpoints (alpha = 0.025 shared):
  - a. Inflammation control
  - b. Antiviral resistance mutations

Gate-keeping procedure:

Primary endpoints must be significant before testing secondaries

Holm-Bonferroni correction within each family

Truncated testing if primary endpoint non-significant

Family-wise error rate controlled at 0.05 using:

Separate error rates for each trial

Sequential gatekeeping

Multiplicity adjustment within families

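### The interim efficacy P-value of 0.0005 agrees with the SAP's spending function only at one-third information, not at the preferred 15 per arm, and no final level allowing for the look is stated

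*SAP*

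**What the plan says.** **Boundary.** SAP 3.5 states that a "flexible alpha spending approach with a power function is suggested". The exponent is 3.561, "chosen so that the two-sided P-value to stop the trial for efficacy is 0.0005 for each comparison". The information fraction behind 0.0005 is not given. Protocol 8.3.1 uses the same function and exponent but gives a stopping P-value of 0.001, with no split by comparison.

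**Timing.** SAP 3.5 puts the look "after one-third (1/3) and before one-half (1/2) of the patients have reached their primary endpoint", "ideally when there are 15 patients per arm", separately for each trial. Protocol 8.3 (Interim Analysis) uses the same window but counts enrolled patients. Protocol 4.1, 8.3.1 and 10.1 say one third, with no range.

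**Final level.** According to SAP 4.1, the primary analysis "will be conducted with a two-sided alpha of 0.05/2 = 0.025 to account for the two primary comparisons of interest". SAP 3.4 promises control for interim analyses and points to details further on, but no later section gives a final boundary.

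**Sample size.** SAP 3.3 plans 117 enrolled and 35 evaluable per arm in Trial I. For Trial II it says: "Given 28 participants per arm (105 total from Trial I with 20% loss to follow-up".

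**The concern.** A spending function produces a boundary that moves with the information fraction, whereas a single printed P-value does not. If the printed value belongs to one fraction and the look is planned at another, the plan contains two efficacy rules. An interim P-value of 0.001 in Trial I at 15 per arm would cross the function's boundary (0.0012) but not the printed one (0.0005). That choice should not be left until someone has seen unmasked data.

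The second issue is the final test. Alpha spent at the look has to come off the final test. SAP 4.1 explains 0.025 entirely by the two comparisons and leaves nothing visible for the look, so a reader following it as written would slightly overspend.

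The third is that the boundary cannot be computed until the information fraction is defined, and in Trial II the plausible denominators give clearly different answers.

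**Working it through.** **Inputs.** Exponent 3.561 (SAP 3.5); alpha 0.025 per comparison (SAP 4.1); 15 per arm at the look (SAP 3.5); Trial I 35 evaluable per arm and 117/3 = 39 enrolled per arm; Trial II 105/3 = 35 planned and 28 evaluable per arm (SAP 3.3).

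**Step 1: reproduce the plan's figure.** At a first look the nominal two-sided P-value equals the alpha spent, alpha × t^3.561.
- SAP: 0.025 × (1/3)^3.561 = 0.00050. This matches.
- Protocol: 0.05 × (1/3)^3.561 = 0.0010. This matches its 0.001.
- The exponent that spends 1/50 of alpha at t = 1/3 is ln(0.02)/ln(1/3) = 3.561.

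Both printed values are therefore the function's value at exactly one-third information. They differ only because one uses alpha 0.025 and the other 0.05.

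**Step 2: fractions implied by 15 per arm.**
- Trial I: 15/35 = 0.429 of evaluable; 15/39 = 0.385 of enrolled.
- Trial II: 15/35 = 0.429 of planned participants (45/105); 15/28 = 0.536 of evaluable (45/84). If the 15 are randomized patients who then suffer the planned 20% loss, 12/28 = 0.429.

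None of these is 1/3.

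**Step 3: boundary, matching final level and total error.** The final level solves P(|Z1| > c1 or |Z2| > c2) = 0.025, with (Z1, Z2) bivariate normal and correlation √t. The last two columns give the total two-sided error per comparison if the final test stays at 0.025.

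| t | Function's interim P | Ratio to 0.0005 | Matching final P | Total error, interim fixed at 0.0005 | Total error, interim from function |
|---|---|---|---|---|---|
| 1/3 | 0.00050 | 1.0 | 0.0247 | 0.0253 | 0.0253 |
| 0.385 | 0.00083 | 1.7 | 0.0246 | 0.0252 | 0.0254 |
| 0.429 | 0.00122 | 2.4 | 0.0244 | 0.0252 | 0.0256 |
| 1/2 | 0.00212 | 4.2 | 0.0241 | 0.0251 | 0.0259 |
| 0.536 | 0.00271 | 5.4 | 0.0239 | 0.0251 | 0.0261 |

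The last row applies only if Trial II information is counted against the 84 evaluable patients.

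**Step 4: joint error over the two comparisons** (2 million simulated trials at each of t = 1/3, 0.429 and 0.536; shared oral arm).
- Final test at 0.025 each (Bonferroni): 0.047 to 0.049, below 0.05.
- Final max-T test at 0.05 with no deduction: 0.0502 to 0.0505 with 0.0005 fixed; with the function, 0.0505 at 1/3, 0.0510 at 0.429 and 0.0520 at 0.536.

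**The case against.** The case for leaving the text alone has real weight.

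- **The 0.0005 may describe calibration.** The wording can be read as explaining how the exponent was picked, with the boundary recomputed at the actual fraction, as is normal under Lan-DeMets. Three Protocol sections place the look at one third, where 0.0005 is right. This is a fair reading, but the SAP never states the reference fraction and prefers a look that is not at one third.
- **The rule is advisory.** The function is only suggested, the decision guidelines are to be agreed at the first DSMC meeting, and a crossing triggers DSMC discussion, not automatic stopping. This limits the harm. It also means that the first meeting should receive one rule, not two.
- **The fixed value is conservative.** A threshold of 0.0005 applied after one third is stricter than the function. A reader might infer that the interim is too lax; it is not.
- **Silence on the final level is not a decision.** A reader might infer that the plan has chosen to ignore the look at the final analysis. SAP 3.4 promises control, and SAP 3.5 refers to group sequential boundaries, which imply a final one. The level is unstated, not declared unadjusted.
- **Trial II and the one-half limit.** A reader might infer that 15 per arm breaks the plan's own upper limit in Trial II. That follows only if the 84 evaluable patients are the denominator. Against the 105 planned it is 43%, inside the window. The SAP's phrase about patients and the Protocol's count of enrolled patients both allow that reading. Direct entry into Trial II also makes the eventual total less certain.

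**Conclusion.** The point stands as a mismatch and an omission. It is not a calculation error, since 0.0005 reproduces at t = 1/3. At the preferred look of 15 per arm in Trial I (t = 0.43) the function's own threshold is 0.0012, which is 2.4 times the printed value; at the upper end of the window it is 4.2 times. The printed value errs on the strict side.

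Following SAP 4.1 literally overspends by at most about 0.001 per comparison within the window. Jointly, the error stays below 0.05 with a 0.025 Bonferroni final test and reaches about 0.051 at t = 0.43 with an undeducted max-T test. The documents do not support a claim of material type I error inflation, nor a firm claim that the Trial II look falls outside its window.

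These figures assume one look per trial, information proportional to patients with outcomes, and normally distributed test statistics. This is a minor correction, worth making before any unmasked interim data are seen.

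**What to change.** 1. Define the information fraction for each trial and name its denominator (evaluable or planned participants). Confirm that 15 per arm falls between one third and one half on that definition in Trial II, and align the Protocol's enrolment-based and one-third wordings with it.
2. State that the interim boundary is computed from the spending function at the observed fraction, with 0.0005 at 1/3, 0.0012 at 0.43 and 0.0021 at 1/2 as examples.
3. State that the final nominal level per comparison is the remaining alpha (0.0247, 0.0244 and 0.0241 respectively), and say how that reduction enters the max-T P-values and simultaneous intervals.
4. Reconcile the Protocol's 0.001 (the same function at overall alpha 0.05) with the SAP's 0.0005 per comparison.

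The changes are to SAP 3.5 and 4.1, the Protocol's interim text and the DSMC guideline. Sample size and design are untouched, and the final level falls by about 0.001 or less (0.025 − 0.0241 = 0.0009 at t = 1/2).
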